9.8. Quality control

9.8.1. Data quality assurance

Data entered manually will be collected via QCTMS EDC™ using eCRFs. Investigator will be responsible for data entry into the QCTMS EDC™ system. Data checks are embedded into the eCRF to remove data entry errors wherever possible. Data will be validated throughout the course of the study (raising queries in QCTMS EDC™ if necessary) according a Data Management Plan. In the event of discrepant data, data clarification will be requested from the sites, which the sites will resolve electronically in the QCTMS EDC™ system. eCRFs and correction documentation will be maintained in the QCTMS EDC™ system's audit trail.

9.8.2. Monitoring

Monitoring activities will be performed by the CRO, as defined in the Monitoring Plan. Each site will be visited at regular intervals by a monitor to ensure compliance with the study protocol and legal aspects. This will include on-site checking of eCRFs for completeness and clarity, cross-checking with source documents, and clarification of administrative matters. In addition, the monitor will review remotely the data entered into the eCRFs on an ongoing basis.

The monitor will follow Standard Operating Procedures (SOPs) of the CRO. The monitor will prepare and submit a written report to the CRO after each study site visit or study-related communication.

9.8.3. Source data / source data verification

Study monitors will perform ongoing source data verification as defined in the Monitoring Plan to confirm that data entered by authorized site staff from source documents into the eCRFs are accurate.

Before study initiation, the types of source documents that are to be generated will be clearly defined in the Monitoring Plan. This includes any protocol data to be entered directly into the eCRFs (i.e., no prior written or electronic record of the data) and considered source data.

Source documents that are required to verify the accuracy of data entered into the eCRFs must not be obliterated or destroyed and must be retained per the policy for retention of records described in Section 9.8.4.

The investigators and institutions must provide the Sponsor's duly authorized personnel, the EC and applicable RAs to have direct access to source data which supports the data on the eCRFs. These personnel, bound by professional secrecy, must keep confidential all personal identity or personal medical information (according to confidentiality rules).

9.8.4. Source data handling and record keeping

The investigator is responsible for keeping all study-related documents (including but not limited to investigators file, source data, compact disc with subject data recorded during the study, signed ICFs, original subject identification list, EC, RA and sponsor correspondence pertaining to the study) in appropriate file folders. The study-related documents must be retained as strictly confidential at the investigator's site for at least 15 years after the completion or discontinuation of the study.

All data and documents shall be made available if requested by relevant Regulatory Authorities or Ethics Committees.

9.8.5. Sponsor audits and inspections by Regulatory Authorities (RA)

Representatives of the Sponsor's clinical quality assurance department may visit the site at any time during or after completion of the study to conduct an audit of the study in compliance with regulatory guidelines and company policy. Similar auditing procedures may also be conducted by agents of any regulatory body.

The investigator agrees to allow the Sponsor auditors/RA inspectors to have direct access to his/her study records for review, being understood that these personnel is bound by professional secrecy, and as such will not disclose any personal identity or personal medical information.

The investigator will make every effort to help with the performance of the audits and inspections, giving access to all necessary facilities, data, and documents.

As soon as the investigator is notified of a future inspection by the authorities, he will inform the Sponsor and authorize the Sponsor to participate in this inspection.

The confidentiality of the data verified and the protection of the subjects should be respected during these inspections.

Any result and information arising from the inspections by the RA will be immediately communicated by the investigator to the Sponsor.

The investigator shall take appropriate measures required by the Sponsor to take corrective actions for all problems found during the audit or inspections.

9.9. Limitations of the research methods

Due to limited data concerning the signal of outcome of interest no test hypothesis for this study has been formulated.

The limitations of this study are characteristic to other studies of a similar design (i.e., real life observational studies). Information concerning the potential confounders will be difficult to control.

Because of non-randomized design, absence of blinding and control group selection bias and information bias may occur. To mitigate this risk and ensure that study population represents the source population, investigators and study sites will be selected randomly from the available list of Slovakian immunologists and allergologists. The investigators will be trained and encouraged to enroll all eligible patients consecutively and keep screening logs to document the number of patients invited (refer to Section 9.2).

Some misclassification of outcome variables as well as confounders is possible. A validation is planned which will assess the rate of misclassification and correct the estimates accordingly. To mitigate the risk of information bias, investigators encouraged to collect as much data concerning the event of interest (adverse renal effects) as possible within the frame of routine practice. A set of available clinical data about the event of interest, presented in a standard format, will be adjudicated by an independent assessor.

Misclassification of exposure is not expected to happen. However due to nature of dosing regimen study population may be not homogenous in terms of duration of treatment and dosing schedule.

Since inclusion and exclusion criteria are very limited, it is expected that enrolled subjects will represent the source population (i.e., target patients of Polyoxidonium therapy) in Slovakia. To document the number of patients invited and assess selection bias in subject recruitment, screening logs will be used.

Subjects included in the study are expected to be representative of the source population (i.e., patients for whom Polyoxidonium is routinely prescribed in Slovakia) in terms of gender, age distribution, socio-economic class, indication, concomitant diseases.

Confounding by known and unknown covariates may happen:

- Patients with variety of diseases and medical conditions are planned to enroll in scope with Polyoxidonium approved indications. Study population will not be homogenous.
- Eligible subjects are likely to receive a concomitant treatment with nephrotoxic medicines, including some antibiotics. It may be impossible to estimate precisely the causative agent of observed adverse renal effects.

Regular medical records at study sites (i.e., primary or secondary health care institutions in Slovak Republic) will be used as data source. The potential for missing data for variables of interest in this setting is unknown, and implications for information bias are to be determined.

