7.2. Rationale of this study

Polyoxidonium has been marketed for almost 20 years (it was first launched in 1996 in Russia). In Slovak Republic, Polyoxidonium is available since 2002. It is estimated that during the period from 1996 to 2013 (inclusive) the total number of approximately 1,025,000 patients worldwide have used Polyoxidonium. No adverse effects specifically affecting any of organ systems have been reported in clinical development programme and during routine post-authorisation pharmacovigilance activities.

Data from Polyoxidonium acute and sub-acute toxicity studies in rodents and chronic toxicity studies in dogs showed the potential risk of nephrotoxicity, which occurred at doses well above the therapeutically relevant dose range. Nephrotoxic effect was observed in dogs after 40 daily injections of Polyoxidonium at doses 10 times exceeding the maximum recommended human dose and in rats after 15 daily injections at doses as high as 100 times the maximum recommended human dose. Besides, Polyoxidonium is predominantly excreted by kidneys.

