9.2.1. Subject inclusion criteria

To be eligible for participation in this study, the patient must:

- (a) be male or female at least 18 years of age.
- (b) receive Polyoxidonium prescription in accordance to the SmPC currently approved in Slovakia, i.e., for the treatment of any of the following diseases or conditions accompanied by secondary immunodeficiency:
 - chronic recurrent bacterial infection;
 - chronic recurrent viral infection;
 - acute bacterial infection;
 - acute viral infection;
 - allergic disease (pollinosis, bronchial asthma, atopic dermatitis).
- (c) be informed about the study and provide written consent to participate.

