9.2.2. Subject exclusion criteria

The patient can't take part in the study if:

- (a) Polyoxidonium is contraindicated as per SmPC:
 - if there is known hypersensitivity to azoximer bromide or any of the excipients of Polyoxidonium;
 - if a woman is pregnant or breast-feeding;
 - if a woman of childbearing potential doesn't use effective contraception method (acceptable methods of birth control are: intrauterine device (IUD), diaphragm

with spermicide, contraceptive sponge, condom, vasectomy, hormonal contraceptive).

- (b) investigator deems necessary to prescribe more than 10 injections of Polyoxidonium per a single treatment course for the given patient.
- (c) patient has any clinically significant underlying medical illness, condition or disorder that, in the judgment of the investigator, could interfere with the conduct of the study.
- (d) patient is currently enrolled in any other investigational study or has participated in a interventional study within 4 weeks before enrolment.

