3. PHARMACEUTICAL FORM

Lyophilisate for solution for injections

Drug description: lyophilisate of yellowish to yellow colour and spongy consistence.

4. CLINICAL PARTICULARS**4.1 Therapeutic indications**

Polyoxidonium 6 mg is indicated in adults for therapy of disease, which are accompanied by secondary immunodeficiency:

- recurrent chronic bacterial infections
- recurrent chronic viral infections
- acute bacterial infections
- acute viral infections
- allergic disturbances (polynosis, bronchial asthma, atopic dermatitis)
- serious septic conditions
- post-surgical complications - purulent affections
- in patients with decreased cell immunity caused by primary therapy (cytostatics, X-ray)

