4.2 Posology and method of administration

Polyoxidonium can be administered in form of either monotherapy or in complex therapy together with antibiotics, antivirals, antimycotics or antihistaminics, broncholytics, corticosteroids, beta-agonists or cytostatics.

Posology

Polyoxidonium is administered to adults depending on the diagnosis and degree of the disease.

Acute inflammatory diseases, complicated forms of allergic disturbances: 6 mg daily for 3 days, then every second day; one cure comprises of 5-10 injections;

Chronic inflammatory diseases: five injections of 6 mg every second day, then twice a week; one cure comprises of 10 injections;

- urogenital diseases: 6 mg every second day, one cure comprises of 10 injections. Concomitant use of chemical drugs is recommended.

- chronic recurrent herpes simplex: 6 mg every second day, one cure comprises of 10 injections, concomitant use of drugs for treatment of herpes is recommended, interferons and interferone inductors.
- allergic disturbances: 6 mg during 2 days, then 6 mg every second day one cure comprises of 5 injections. The drug should be administered concomitantly with the antihistamine and other antiallergic drugs.
- oncological diseases: prior and after chemotherapy 6-12 mg every second day, one cure comprise of at least 10 injections.
- correction of immunodeficiency in patients with decreased cell immunity caused by primary therapy: 6 mg once to twice a week, 2-3 months to 1 year.

Experiences with the use in children are limited.

Method of administration

Dissolve the content of vial (ampoule) in 1.5 – 2 ml water for injections or isotonic saline solution. The solution should be clear, without any mechanical impurities. Do not administer turbid solution.

The drug product should be administered intramuscularly, the slow application for 15-20 second is recommended. Intramuscular injection site should be deltoid muscle of upper limb or outer quadrant of thigh muscle.

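### The protocol expects its sample to represent Slovak Polyoxidonium patients, including by indication, but it enrols five of the eight SmPC indications and no planned course above 10 injections, and lists neither restriction as a limitation

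*Protocol*

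**What the plan says.** Section 8 sets the research question as safety under routine prescribing within the marketing authorisation and makes the study part of the Risk Management Plan.

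Inclusion criterion (b) in Section 9.2.1 requires that patients "receive Polyoxidonium prescription in accordance to the SmPC currently approved in Slovakia, i.e., for the treatment of any of the following diseases or conditions" that follow. Five are listed: chronic recurrent bacterial infection, chronic recurrent viral infection, acute bacterial infection, acute viral infection, and allergic disease.

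Exclusion criterion (b) in Section 9.2.2 applies where the "investigator deems necessary to prescribe more than 10 injections of Polyoxidonium per a single treatment course for the given patient". Section 9.2.4 attributes a course of 5-10 injections to the SmPC, and Section 9.2.6 lists five regimens within that range.

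Section 9.9 concludes that "it is expected that enrolled subjects will represent the source population (i.e., target patients of Polyoxidonium therapy) in Slovakia". The reason it gives is the small number of eligibility criteria: "Since inclusion and exclusion criteria are very limited". Section 9.2 makes the same argument. Section 9.9 adds that subjects should be representative "in terms of gender, age distribution, socio-economic class, indication, concomitant diseases".

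The SmPC in Annex 4 is wider. Its section 4.1 has eight indications. Its section 4.2 has seven regimens, among them an oncological course of at least 10 injections and a course for decreased cell immunity after primary therapy of "6 mg once to twice a week, 2-3 months to 1 year".

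**The concern.** The representativeness statement claims a property that eligibility does not deliver. Inclusion (b) reads as a restatement of the SmPC but is a subset of it, and the course length attributed to the SmPC leaves out its two longest regimens. A reader of Section 9.9 would not learn that three labelled indications and most long courses lie outside the study.

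This matters because of how the result may be used. Section 9.1 gives evidence about the absence of risks as one purpose. A result with no renal cases would inform short courses in five indications, while the protocol's text invites reading it for the drug's target patients generally. One omitted indication also bears on the planned analysis. Section 9.7.1 stratifies renal effects by nephrotoxic co-medication, and Annex 3 counts cisplatin, carboplatin, ifosfamide and methotrexate among nephrotoxic drugs. Patients immunosuppressed by cytostatics are a group in which such co-medication would be expected.

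**Working it through.** **1. The plan's own figure: 5-10 injections per course.** The five regimens in Section 9.2.6 give 5-10 (acute inflammatory disease or complicated allergy), 10 (chronic inflammatory), 10 (urogenital), 10 (recurrent herpes simplex) and 5 (allergic). The range is 5-10, so the figure reproduces for those five. SmPC 4.2 has two more regimens (oncological; decreased cell immunity after primary therapy), so the figure covers 5 of 7 and is not the SmPC range.

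**2. Indications.**

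| SmPC 4.1 | In inclusion (b)? |
|---|---|
| Recurrent chronic bacterial infection | yes |
| Recurrent chronic viral infection | yes |
| Acute bacterial infection | yes |
| Acute viral infection | yes |
| Allergic disease | yes |
| Serious septic conditions | no |
| Purulent post-surgical complications | no |
| Decreased cell immunity from cytostatics or X-ray | no |

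8 - 5 = 3 are absent. This counts label entries, not patients.

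**3. Length of the long SmPC course.** Injections = injections per week × weeks, with 2 months = 2 × 52/12 = 8.7 weeks, 3 months = 13 and 1 year = 52. Total dose = injections × 6 mg.

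| Duration | Once weekly | Twice weekly |
|---|---|---|
| 2 months | 8.7 (52 mg) | 17.3 (104 mg) |
| 3 months | 13 (78 mg) | 26 (156 mg) |
| 1 year | 52 (312 mg) | 104 (624 mg) |

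The range is about 9 to 104 injections.

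**4. Against the cap.** An enrolled course has at most 10 injections, or 10 × 6 = 60 mg under the regimens in Section 9.2.6. The eleventh injection falls in week 11 at once weekly and in week 6 at twice weekly (11/2 = 5.5). Of the six combinations above, only once weekly for 2 months stays under the cap. The oncological regimen starts at 10 × 6 = 60 mg to 10 × 12 = 120 mg. A course of exactly 10 is not caught by exclusion (b), but oncology is not a listed indication.

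**5. What a clean result would mean.** Assume that all 500 expected subjects (Section 9.5) are evaluable and none has an adverse renal effect. The one-sided 95% upper limit is 1 - 0.05^(1/500) = 0.0060, or 0.60%. It would apply to courses of at most 10 injections in the five listed indications, and to nothing else in the SmPC.

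**6. Limitations section.** Section 9.9 mentions possible selection bias and varying treatment duration and dosing schedule among enrolled subjects. It does not mention the omitted indications or the cap.

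**The case against.** Much can be said for the protocol. The five indications and the cap are stated openly, and restricting a population is legitimate. The source population is described as patients routinely prescribed the drug in Slovakia, and sites are drawn at random from the specialists said to be its usual prescribers. If those specialists rarely treat the omitted indications, little is lost. SmPC entries also overlap: some septic or post-surgical patients might enter as acute bacterial infection, although the text does not say so. Screening logs are planned to assess selection. All of this stands as a limit on the size of the problem. It does not supply the missing statement of scope, and the logs are described only as documenting the number of patients invited.

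Several stronger readings are tempting and are not supported:

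- **That the protocol claims to represent all patients treated under the SmPC.** It does not say so; it speaks of target or routinely treated patients in Slovakia.
- **That the excluded courses are the exposure closest to the animal renal signal.** Section 7.2 does say "Nephrotoxic effect was observed in dogs after 40 daily injections of Polyoxidonium", at 10 times the maximum human dose. It also reports a rat signal after 15 daily injections at 100 times that dose, says that intervals between injections markedly reduced the effect, and reports no kidney damage in rats given 100 times the dose for 3 months with intervals. The long SmPC course is spaced 3.5-7 days apart, whereas some enrolled regimens begin with 2-3 daily injections. The excluded courses are the longest and highest in cumulative dose, which is a narrower statement.
- **That the study sees only 10-40% of a long course.** That takes twice-weekly dosing for 3 months (10/26 = 38%) to 1 year (10/104 = 10%). A once-weekly 2-month course of about 9 injections fits wholly under the cap.
- **That all three omitted indications involve long exposure.** SmPC 4.2 gives no long course specific to septic or post-surgical patients.

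**Conclusion.** The point holds as a contradiction between the stated and the actual study population. Five of eight SmPC indications and five of seven SmPC regimens are covered, and planned courses above 10 injections are excluded, against an SmPC range that reaches about 104 injections. Section 9.9 nevertheless expects representativeness, by indication too, on the ground that the criteria are few.

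The counts come directly from the documents; the injection totals rest on the week conversions shown. The number of patients affected cannot be estimated, because the protocol does not say how often participating practices use the drug for the omitted indications or for longer courses. The selection effect may be large or negligible. What is established is that the conclusion's scope is stated more widely than the design allows. It should be corrected before the study is read as evidence on renal safety.

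**What to change.** Reconcile Sections 9.2.1, 9.2.4, 9.2.6 and 9.9 with SmPC 4.1 and 4.2. This concerns the scope of inference and implies no view on which indications or regimens should be used.

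- In Sections 8, 9.2 and 9.9, define the source population as adults given a course of at most 10 injections for one of the five listed indications by immunologists or allergologists. Keep the representativeness statement, limited to that frame; random site selection and consecutive enrolment can still support it there.
- In inclusion (b), replace the wording that equates the five indications with the SmPC by wording that shows them as a subset. In Sections 9.2.4 and 9.2.6, describe 5-10 injections as the range of the regimens studied. Align the abstract.
- In Section 9.9, list both restrictions as limitations, and state that no safety conclusion, including absence of renal effects, extends to longer courses or to the omitted indications.
- Optionally, record on the screening log how many patients are ineligible because of indication and how many because of planned course length. This extends the log beyond patients invited, but it would give the only figure on the size of the selection effect.

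The cost is a narrower conclusion and slightly more logging. Enrolment and treatment are unchanged.

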9.10. Other aspects

9.10.1. End of the study

The end of study is the date of the last visit of the last subject undergoing the study.

Early study termination decided by the Sponsor

The Sponsor reserves the right to prematurely stop or to interrupt the study at any time and for any reason; the decision will be communicated in writing to the investigator.

Early study termination decided by the RA/EC

The RA/EC may suspend or prohibit a study if it considers that the conditions of authorisation are not being met or has doubt about the safety or scientific validity of the study.

Early study termination decided by the investigator

The investigator must notify (30 days' prior notice) the Sponsor of his/her decision and give the reason in writing.

In all cases (decided by the Sponsor or by the investigator), the appropriate Regulatory Authorities and Ethics Committees should be informed.

Termination of the study in an individual case

Every subject has a right at any time and without indicating any reasons to withdraw his/her consent for further participation in the clinical study. Other possible reasons of subjects withdrawal from the study and procedures for discontinuation are described in Section 9.2.3.

10. PROTECTION OF HUMAN SUBJECTS**10.1. Ethical principles**

This study will be conducted in accordance with principles stated in the Declaration of Helsinki and subsequent amendments and in accordance with Guideline on Good Pharmacovigilance Practices (GVP) Module VIII-Post-authorisation safety studies [1], Good Pharmacoepidemiology Guidelines (GPP) [2] and Guide on Methodological Standards in Pharmacoepidemiology from The European Network of Centers for Pharmacoepidemiology and Pharmacovigilance (ENCePP) [3].

Before initiating the study, this study protocol will be submitted to the Slovakia State Institute for Drug Control and relevant ethics committees.

The study will start only after obtaining written approvals from the corresponding institutions.

